	
h. Bladder stones
 
7. Dependence on an electro-magnetic medical implant (e.g. cardiac pacemaker or implanted drug pump) or external device
 
8. Any unsuitable comorbidities as determined by the Investigator or complications related to use of certain medications
 
9. Any physical or cognitive impairments that diminish the subject's ability to follow directions or otherwise safely use the Gen 2 Connected Catheter System
 
10. Catheter Assessment Tool screening yields unacceptable results

Primary Efficacy Endpoint	
Primary efficacy: Post-void residual urine volume (PVR) with the use of the Connected Catheter
 
A subject is considered a responder to the treatment if a minimum of 80% of their PVR values met the following criteria
 
PVR is <math>\leq</math> 50 mL OR
 
PVR is <math>\leq</math> baseline PVR with the standard of care catheter
 
If a subject drops out before the conclusion of the study after passing the Device Tolerability Screening, their PVR data will still be included in the primary analysis.

Primary Safety Endpoint	Rate of device related SAE
Secondary End Points	
 
1. Successful device insertion, anchoring, and removal
 
2. Successful sealing of the catheter valve
 
3. Quality of life improvement as measured by SCI-QOL Survey
 
4. UTI occurrence rate
 
5. Lower Urinary Tract injury rate
 

Study and Data Management	
Spinal Singularity, Inc.
 
[name]
 
[name]
 
[contact]
 
Fax: + 1 [contact]

Study Safety Monitor	
[name], MD,
 
Professor of Urology and Radiology Chairman,
 
Department of Urology

	University of California, Irvine
--	----------------------------------

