#### **8.5.2 Primary Safety**

Any adverse events and serious adverse events related to the use of the investigational device will be analyzed with descriptive statistics and nominal 95% confidence interval. There will be no formal statistical hypothesis test for primary safety.

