## **9.4 Test Phase**

The Test phase will require three (3) Exchange Appointments and a final Removal Appointment. Each appointment will assess PVR, voided volume, quality-of-life (QOL), and urinary tract injury, adverse events, medication, and other study assessment. Additionally, the subjects will be asked to fill out a User Experience Survey and Safety and Performance Survey and the device will be evaluated for fit, migration, placement, and removal.

At each exchange visit, the clinic research staff will follow these procedures:

1. Patient Arrival – Vital Signs and other measurements
2. Bladder Volume – Measurement using Ultrasound to ensure at least 200 mL of urine
3. Patient empties bladder – PVR volume measurement using Ultrasound
4. Patient removes Connected Catheter
5. Patient waits for bladder to fill – additional surveys completed
6. Patient inserts new Connected Catheter and bladder emptied – PVR volume measured
7. Patient Departure

For the final device removal visit the clinic research staff will follow these procedures:

1. Patient Arrival – Vital Signs and other measurements
2. Bladder Volume – Measurement using Ultrasound to ensure at least 200 mL of urine
3. Patient empties bladder – PVR volume measurement using Ultrasound
4. Patient removes Connected Catheter
5. Patient completes all surveys
6. Patient departure

Once the patient completes the final device removal visit the patient will enter the follow-up phase.

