### 10.3 Statistical Analysis

Data from all the sites will be pooled together assuming poolability analysis show that the data are poolable.

The primary efficacy endpoint will be hypothesis tested based on the mITT population. An analysis of all subjects that dropped out during or after the device tolerability screening will be provided.

The primary efficacy outcome will be assessed using an exact binomial test at the 0.05 significance level, in a one-sided test of the null hypothesis that the user responder rate is 0.60 or less, against the alternative hypothesis that the user responder rate is greater than 0.60.

For the primary safety endpoint, device related SAE will be analyzed with descriptive statistics and nominal 95% confidence intervals. Serious adverse events from all subjects that were treated with the investigational device will be included. Based on the sample size calculations, the source of the SAE will be from all 60 subjects that tested the device. There will be no formal statistical hypothesis testing.

Similarly, the secondary endpoints will be analyzed with descriptive statistics and nominal 95% confidence intervals.

Tipping point analyses will be conducted to investigate issues such as the possible impact of missing data.

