### 11.8.1 Device and Procedure-Related Adverse Event

A description of how an AE relates to the study procedure will be reported on the Adverse Event eCRF and starts from the first use of the device and be determined by the Investigator using the following definitions:

- **Definite:** The AE follows a reasonable temporal sequence from the time of the first insertion procedure, which includes AEs that occur during the index procedure or during the follow-up period.
- **Probable:** The AE follows a reasonable temporal sequence from the time of the first insertion procedure, and the possibility can be excluded that factors other than the index procedure, such as underlying disease, concomitant drugs, or concurrent treatment caused the AE.
- **Possible:** The AE follows a reasonable temporal sequence from the time of the first insertion procedure and the possibility of insertion procedure involvement cannot be excluded. However, other factors such as underlying disease, concomitant medications, or concurrent treatment are presumable.
- **Unlikely:** The AE has an improbable temporal sequence from the time of the first insertion procedure, or such AE can be reasonably explained by other factors, including underlying disease, concomitant medication, or concurrent treatment.
- **Not related:** The AE has no temporal sequence from the time of the first insertion procedure, or it can be explained by other factors, including underlying disease, concomitant medication, or concurrent treatment.

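### The only defined relatedness scale is tied to the first insertion rather than to the device, so the device-related SAE rate can err in either direction

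*Combined protocol and SAP*

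**What the plan says.** The synopsis gives the primary safety endpoint as "Rate of device related SAE". Section 8.5.2 words it more broadly: "Any adverse events and serious adverse events related to the use of the investigational device will be analyzed with descriptive statistics". Section 10.3 returns to SAEs only: "device related SAE will be analyzed with descriptive statistics and nominal 95% confidence intervals". There is no hypothesis test.

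Relatedness is dealt with in three places:

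- Section 11.7 has the investigator assign each event to a primary cause. The investigational device and the insertion procedure are separate categories. No criteria are given.
- Section 11.8 lists relationship to the study device among the items recorded for every AE, again without criteria.
- Section 11.8.1 supplies the only graded scale with definitions. Its heading names both device and procedure, but it opens: "A description of how an AE relates to the study procedure will be reported on the Adverse Event eCRF". All five grades, from Definite to Not related, are timed from the first insertion. Probable requires that "the possibility can be excluded that factors other than the index procedure" are responsible. Possible turns on whether involvement of the insertion procedure can be ruled out. Unlikely applies when "The AE has an improbable temporal sequence from the time of the first insertion procedure", or when other factors explain the event.

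Use of the device goes well beyond one insertion. After a tolerability screening of up to one week, section 9.4 states: "The Test phase will require three (3) Exchange Appointments and a final Removal Appointment".

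**The concern.** The endpoint concerns the device, while the defined scale concerns one procedure on one day. No grade mentions wearing the catheter, operating the valve, a later exchange or a removal. Yet section 7.1 says complications may arise during insertion, use or removal, and its entry on hematuria names removal, migration and sizing among the device-related causes.

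The anchor is also unrepresentative of how the device is used. Under section 9.2.1 a trained clinician performs the first insertion. Under sections 8.3 and 9.4 the subjects themselves remove and insert later catheters, under supervision.

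With about two dozen treated men and no formal test, the safety result is a small count and an interval. If the rule for membership of that count is unclear, two investigators can record the same event differently, and the published rate depends on which reading each site adopted.

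**Working it through.** The plan states no expected SAE rate and no figure for relatedness, so there is no figure to reproduce. The check is first a reading of the definitions and then an illustration of scale.

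**Step 1. Pass one event through the scale.** Take an SAE plainly caused by removal of the last catheter, about five weeks after the first insertion (one week of screening plus four of the Test Phase).

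- Definite: requires only plausible timing after the first insertion and expressly reaches into follow-up. Available if any later time counts as plausible.
- Probable: requires that factors other than the index procedure be excluded. The cause is a removal, so read literally it fails.
- Possible: requires that involvement of the insertion procedure cannot be excluded. Where the removal is clearly the cause, it fails.
- Unlikely: available if five weeks after the first insertion is judged improbable timing.
- Not related: available if the removal is treated as another explanatory factor.

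The two middle grades are closed, and grades at both ends are open. Harm from wear or valve operation meets the same difficulty.

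**Step 2. Look for a rule that resolves it.** Sections 11.7 and 11.8 could place this event under the device. Section 10.3 does not say whether the rate is built from the primary-cause category, the relationship item or the 11.8.1 grade, nor where on the scale relatedness begins. The documents contain no such rule.

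**Step 3. Share of insertions at the anchor.** Inputs: 24 men expected to enter tolerability screening and 16 evaluable (section 8.8). The step reproduces: 24 × (1 − 0.33) = 16.08. A completer uses five catheters: one in screening, one on entering the Test Phase and three at exchanges.

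- If all 8 dropouts use one catheter only (an assumption; section 8.8 places dropout after the tolerability screening without giving a week): 16 × 5 + 8 × 1 = 88 insertions. First insertions are 24/88 = 27%, and later ones 64/88 = 73%.
- If all 24 used five catheters: 24 × 5 = 120, and 24/120 = 20%.

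Size changes under section 9.2.3 would add insertions. These shares describe exposure outside the anchor. They do not estimate how many SAEs would be misgraded.

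**Step 4. Effect of one regraded SAE.** Exact (Clopper-Pearson) 95% intervals, for both denominators the plan offers:

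| Denominator | One SAE counted | None counted |
|---|---|---|
| 24 (section 8.8) | 4.2% (0.1 to 21.1) | 0% (0 to 14.2) |
| 60 (section 10.3) | 1.7% (0.04 to 8.9) | 0% (0 to 6.0) |

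The conflict between 24 and 60 is a separate matter; both are shown so that the illustration does not depend on it.

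**The case against.** The strongest reply is that section 11.8.1 does not stand alone. Section 11.7 separates device from insertion procedure, section 11.8 requires relationship to the study device for every AE, section 8.5.2 speaks of use of the device, and section 16.1 has an independent monitor adjudicate serious events. A device-caused SAE at a later exchange could be counted through any of these. This stands: a reader might infer that the plan never asks about the device, and that would be wrong. What remains is that these items carry no criteria and are not linked to the primary safety rate. The monitor is to adjudicate under the protocol's own guidelines, so adjudication inherits the same definitions.

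A second reply is that the first insertion merely opens the observation window. The lead-in to section 11.8.1, which starts assessment at first device use, supports this, as does the reach of Definite into follow-up. The alternative causes it lists are disease, drugs and concurrent treatment, not a worn catheter. This also stands in part, and it rules out a tempting inference, that the rate is biased towards zero. On the window reading almost any later event has suitable timing and Definite has no causal test, so the scale can over-include as easily as it can miss events. The causal tests in Probable and Possible still name only the procedure.

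Third, the contrast of one SAE with none would describe any single misclassified SAE. That is correct; it shows how sensitive the endpoint is, not how often the error would occur.

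**Conclusion.** The concern holds as a defect of definition. The only graded scale with criteria measures relation to a procedure, timed from the first insertion, while the primary safety endpoint is about the device; and no rule says which field or grades make an SAE device related. Serious harm from wear, operation, later exchange or removal can be graded out, and events can be graded in on timing alone. The direction of the net error is undetermined.

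At the planned size one grading decision moves the point estimate by 4.2 percentage points with 24 treated, or 1.7 with 60. The definitional finding rests on the text alone. The 27% share rests on the dropouts stopping in week 1 and on no resizing, and falls towards 20% if they stay longer.

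**What to change.** In section 11.8.1, define two separate gradings:

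- relatedness to the device, covering insertion, wear, operation, exchange or removal of any Connected Catheter, IR Tool or Controller;
- relatedness to any insertion procedure, not only the first.

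Judge timing against any relevant exposure, including earlier catheters. Timing from the latest exposure alone could demote delayed or cumulative harm such as stricture. Add a causal criterion to Definite, so that timing alone does not suffice. Identify the device grading as the item that section 11.8 calls for.

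In section 10.3, state that the primary safety rate uses the device grading and which grades count, for example Possible or higher.

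The cost is protocol and eCRF wording, and the reported rate may change. The definitions should be settled before events are graded, because regrading once results are known would be open to challenge.

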### 11.8.2 Concomitant Medication-Related Adverse Event

An adverse event is considered to be concomitant medication related when, in the judgment of the Investigator, it is reasonable to believe that the event is associated with concomitant medications used in conjunction with the Investigational Device and is not otherwise specific to the Investigational Device (e.g. bleeding associated with anticoagulation medication).

### 11.8.3 Pre-Existing Condition-Related Adverse Event

An adverse event is considered to be related to a pre-existing condition when, in the judgment of the Investigator, it is reasonable to believe that the event is associated with the subject's pre-existing condition and is not specific to the Investigational Device or Insertion Procedure. Pre-existing conditions that are aggravated or become more severe during or after the Insertion Procedure should be evaluated on a case-by-case basis to determine if the event may be more appropriately classified as device or Insertion Procedure-related.

## 11.9 Anticipated Adverse Events

The following is a list of potential anticipated adverse events that may occur while using the Connected Catheter.

1. Asymptomatic Bacteriuria
2. Autonomic Dysreflexia (for individuals with spinal cord injury)

3. Bladder or Urethral Perforation (False Passage)
4. Bladder or Urethral Spasms
5. Change in frequency or urgency to urinate
6. Discharge or Cloudy Urine
7. Discomfort
8. Dysuria (Painful Urination)
9. General Fever
10. Genitourinary pain
11. Hematuria (Blood in Urine)
12. Injury to the Lower Urinary Tract (LUT) and/or Genitals
13. Interference with Sexual Activity
14. Part or All of the Connected Catheter Becoming Temporarily Stuck in the LUT
15. Scarring of LUT
16. Systemic Infection
17. Urinary Incontinence
18. Urinary Retention
19. Urethral Stricture
20. Urinary Tract Infection
21. Urinary Tract Inflammation or Irritation

## 12 TRAINING

The Sponsor will be responsible for training of appropriate clinical site study personnel. To ensure proper procedural technique, uniform data collection and protocol compliance, the Sponsor will present a formal training session to personnel at each study site. At this training session, the study protocol, techniques for the identification of eligible subjects, instructions on data collection, schedule follow-ups, and regulatory requirements will be reviewed.

The training of clinical site personnel will be the responsibility of Spinal Singularity (Sponsor). This procedure may only be performed by qualified Investigators who are familiar with the Connected Catheter procedures and techniques. A formal training program consisting of instructive and interactive sessions will be performed with participating Investigators and study personnel identified at each site prior to subject treatment. Spinal Singularity-affiliated personnel will be available to assist with the technical aspects of the device/procedure training, as well as protocol-related training. During the Site Initiation Visit (SIV) or other site visit, training related to specific procedures for using the EDC system such as entering and editing eCRF data, and reviewing and resolving queries will be provided to investigative sites. This training will be documented on a training record. It is ultimately the responsibility of the Investigator to ensure that all clinical site personnel participating in this study are properly trained.

## 13 DATA MANAGEMENT

### 13.1 Subject Identification

Subjects that successfully pass the screening tests and wish to participate in the study will be assigned a unique identification code (ID) that is numeric.

In addition to the ID, each subject's initials will be used as an identifier included on documentation submitted to the Sponsor, as applicable.

### 13.2 Central Database

Applicable study documentation will be collected and compiled in a central database or in hard copy files, as applicable. Appropriate quality control measures will be established to ensure accurate and complete transfer of information from the study documentation to the central database or other document location(s).

The Investigator or designee must record the information required by this clinical investigation protocol in source documentation that must be made available to Sponsor representative or designee for review. An authorized site representative will enter all applicable data into a 21 CFR 11 compliant Electronic Data Capture (EDC) system via Electronic Case Report Forms (eCRFs).

### 13.3 Data Monitoring and Quality Control

Spinal Singularity, Inc. will designate a qualified Monitor (Clinical Research Associate [CRA]) to verify that study data is supported by adequate source documentation, which is complete, accurate and verifiable. Instances of inconsistent, missing or illogical data will be communicated to the Investigator or designee and queried for resolution.

Completed eCRFs will be verified by the qualified CRA at the investigational sites at regular intervals throughout the study. The Investigator will allow the monitor and/or representative of the Sponsor, and any regulatory body to review and inspect the study files, subject eCRFs, subject medical records and other study related documents as required.

Spinal Singularity, Inc. will monitor and manage the data for this investigational study.

The main clinical contact at Spinal Singularity, Inc. will be:

[name]  
[[contact]](mailto:[contact])  
[contact]

The alternate clinical contact at Spinal Singularity, Inc. will be:

[name]  
[[contact]](mailto:[contact])  
[contact]

All general Study inquiries may also be sent to [[contact]](mailto:[contact])

Data will be reviewed periodically by an independent research monitor and a Data and Safety Monitoring Board (DSMB). These monitors will ensure overall safety of the study by analyzing any potential trends or issues that result during the study. The research monitors will assist the Sponsor in ensuring safe execution of this clinical investigation protocol and, if any issues arise, help determine any time when it may be necessary to temporarily halt the study.

The Independent Safety Monitor for the Study will be:

[name], MD,  
Professor of Urology and Radiology Chairman,  
Department of Urology  
University of California, Irvine

## 14 STUDY RESPONSIBILITIES AND MANAGEMENT

The proposed study will be performed in accordance with all requirements set forth in the U.S. regulations, 21 Code of Federal Regulations (CFR) Parts 812.2(b), 50, 54, and 56, the World Medical Association Declaration of Helsinki, EN ISO 14155:2011 (as applicable) and any other applicable local laws, regulations, or guidelines.

### 14.1 Investigator Responsibilities

Each investigator is responsible for ensuring the investigation is conducted according to all signed agreements, this clinical investigation protocol, EC/IRB requirements, and applicable laws and regulations. Also, Investigators may not begin enrollment until Sponsor or its designee receives and approves (when necessary) the following documents:

- Signed Investigator Agreement
- Financial disclosure forms for all participating investigators
- EC/IRB roster (or IRB registration number from the Office of Human Research Protection)
- EC/IRB protocol and ICF approvals
- Investigators' current curricula vitae (CV)
- Signed Site Delegation of Authority (DOA) Log

It is acceptable for Investigators to delegate one or more of the above functions to an associate or Co or Sub-Investigator, or a trained Study Coordinator; however, the Investigator remains responsible for the proper conduct of the clinical investigation, including obtaining and documenting proper study informed consent, collecting all required data, submitting accurate and complete eCRFs, etc.

At each study site, appropriate procedures must be followed to maintain subject confidentiality according to appropriate local regulations (e.g., Health Insurance Portability and Accountability Act (HIPAA) in the U.S.). Each site may have its own internal procedures or requirements for use and release of subject medical information in research studies. Each Investigator is responsible for obtaining appropriate approvals, consents, or releases of medical information as dictated by their relevant subject privacy laws.

The study is not transferable to other sites attended by the Investigator unless prior approval is obtained from the appropriate EC/IRB and the Sponsor.

## 14.2 Subject Enrollment Process

All study candidates, after pre-screening, must appropriately consent to participate in the study, as administrated by qualified study site personnel using an IRB and Sponsor-approved informed consent form (ICF) prior to beginning any aspect of the study procedure or tests that are not standard of care for the site. Investigational sites will be required to document the consent process within each enrolled subject's medical record. Administering the questionnaires can be done prior to signing the ICF.

Only subjects who meet the inclusion/exclusion criteria, who signed the study enrollment informed consent will be considered enrolled in the study.

Timely communication by each site is critical to avoid over enrolling when the enrollment is close to the end of each phase.

